8.2 Responsibility for Analyses/In-House Blinding

The statistical analysis of the data obtained from this study will be the responsibility of the Clinical Biostatistics department of the Sponsor.

This trial is being conducted as a single arm, open-label study, i.e., subjects, investigators, and Sponsor personnel will be aware of subject treatment assignments after each subject is enrolled and treatment is assigned.

8.3 Hypotheses/Estimation

Objectives, hypothesis, and associated estimations of the study are stated in Section 3.

8.4 Analysis Endpoints

Efficacy and safety endpoints that will be evaluated are listed below.

8.4.1 Efficacy Endpoints

Efficacy endpoints that will be evaluated are listed below, followed by the descriptions of the derivations of selected endpoints.

The primary efficacy endpoint is the ORR for each cohort, defined as the proportion of subjects in the analysis population who have CR or PR at any time during the study, prior to disease progression. For rrPMBCL, response assessment will be based on IWG criteria (Cheson, 2007 [1]) using independent central review. For subjects with rrRS, IWG criteria with special considerations for RS will be used (Section 12.7). A secondary efficacy endpoint is ORR based on investigator assessment.

Other secondary efficacy endpoints include: (1) PFS, defined as the time from first dose of pembrolizumab to the first documented disease progression or death due to any cause, whichever occurs first; (2) DOR, defined as time from first response (CR, PR) to disease progression in subjects who achieve a PR or better, (3) DCR, defined as the proportion of subjects in the analysis population who have CR, PR, or SD at any time during the study prior to disease progression and (4) OS, defined as time from first dose to date of death.

PFS, DOR, and DCR will be based both on central review (primary) and investigator assessment (secondary).

Exploratory efficacy endpoints include ORR, PFS, DOR, and DCR, incorporating response assessments for subjects continuing pembrolizumab treatment after initial progression. An additional exploratory endpoint is the ORR based on the Lugano classification [2] using independent central review.

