- a. In subjects who discontinue study therapy without documented disease progression, every effort should be made to continue monitoring their disease status by radiologic imaging every 12 weeks (\pm 7 days) until (1) the start of new anti-cancer treatment, (2) documented disease progression by investigator assessment, (3) death, or (4) the end of the study, whichever occurs first.
- b. After the start of new anti-cancer treatment or documented disease progression by investigator assessment, the subject will transition to the Survival Follow-up and should be contacted by telephone (or in person if recent contact for other purposes during window) approximately every 12 weeks to assess survival status. Updated survival status may be requested by the Sponsor at any time during the course of the study. Upon Sponsor notification, all subjects who do not/will not have a scheduled study visit or study contact during the Sponsor-defined time period will be contacted for their survival status (excluding subjects who have a death event previously recorded).
- c. If subjects have stable disease, partial remission, or complete response they should continue on every 12 week (\pm 7 days) assessment schedule as described in section 7.1.2.7.4. Imaging should occur at any time where there is clinical suspicion of progression.
- d. In subjects with an unconfirmed PD assessment who continued study therapy, a radiological assessment should be performed 12 weeks (\pm 7 days) later or at the time of treatment discontinuation. If previous scan was obtained within 4 weeks prior to the date of discontinuation, then a repeat scan at treatment discontinuation isn't mandatory. However, imaging should occur at any time where there is clinical suspicion of progression.
- e. For women of reproductive potential, a urine pregnancy test should be performed within 72 hours prior to each cycle of trial treatment. If urine pregnancy results cannot be confirmed as negative, a serum pregnancy test performed by the local study site laboratory will be required. Pregnancy tests (serum and/or urine tests) should be repeated if required by local guidelines.

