7.1.2.7.4 Disease Response Assessments/Imaging During the Trial

Following screening, disease response assessments will occur at Week 12 (± 7 days) and every 12 weeks (± 7 days) as detailed in the Trial Flow Chart in Section 6.0. The first

assessment may be performed earlier than 12 weeks if, in the opinion of the investigator, the subject is clinically progressing.

Imaging assessments should be performed (every 12 weeks from the first dose of study medication). There is a ± 7 day window for assessments performed after entry in the study. If PET and CT scan at Screening are negative for disease involvement in the neck, subsequent CT scans may not include neck. If PET or CT scans at Screening are positive for disease involvement of the neck, subsequent CT scans must include neck. Following screening, CT scans should be repeated every 12 weeks for subsequent assessments. PET should be repeated at Week 12, Week 24, or to confirm CR and as clinically indicated. PET to confirm PD is strongly encouraged, but not required, if CT clearly demonstrates PD. Disease assessments and imaging should not be delayed for delays in cycle starts.

Disease assessments and imaging should continue to be performed until documented disease progression by investigator assessment, the start of new anti-cancer treatment, withdrawal of consent, death, or the end of the study, whichever occurs first.

During Second Course, imaging should continue to occur every 12 weeks (+/- 7 days) following the same parameters listed above.

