8.6.1.2 Disease Control Rate

The DCR, defined as the proportion of subjects in the analysis population who have achieved a CR, PR or SD response prior to disease progression. The analysis will consist of the point estimate and 90% 2-sided exact CI; analogous to ORR, an exploratory analysis of DCR will be performed to consider subjects who continue to receive pembrolizumab and later achieve PR, CR or SD following initial progression.

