12.7 Lymphoma Disease Response Criteria

Additional information is located in the Site Imaging Charter.

Criteria for lymphoma disease assessment:

Response	Definition	Nodal Masses	Spleen, Liver	Bone Marrow
CR	Disappearance of all evidence of disease	(a) FDG-avid or PET positive prior to therapy; mass of any size permitted if PET negative (b) Variably FDG-avid or PET negative; regression to normal size on CT	Not palpable, nodules disappeared	Infiltrate cleared on repeat biopsy; if indeterminate by morphology, immunohistochemistry should be negative
PR	Regression of measurable disease and no new sites	> 50% decrease in SPD of up to 6 largest dominant masses; no increase in size of other nodes (a) FDG-avid or PET positive prior to therapy; one or more PET positive at previously involved site (b) Variably FDG-avid or PET negative; regression on CT	> 50% decrease in SPD of nodules (for single nodule in greatest transverse diameter); no increase in size of liver or spleen	Irrelevant if positive prior to therapy; cell type should be specified
SD	Failure to attain CR/PR or PD	(a) FDG-avid or PET positive prior to therapy; PET positive at prior sites of disease and no new sites on CT or PET (b) Variably FDG-avid or PET negative; no change in size of previous lesions on CT		
Relapsed disease or PD	Any new lesion or increase by > 50% of previously involved sites from nadir	Appearance of a new lesion(s) > 1.5 cm in any axis, > 50% increase in SPD of more than one node, or > 50% increase in longest diameter of a previously identified node > 1 cm in short axis Lesions PET positive if FDG-avid lymphoma or PET positive prior to therapy	> 50% increase from nadir in the SPD of any previous lesions	New or recurrent involvement

Abbreviations: CR, complete remission; FDG, [¹⁸F]fluorodeoxyglucose; PET, positron emission tomography; CT, computed tomography; PR, partial remission; SPD, sum of the product of the diameters; SD, stable disease; PD, progressive disease.

Special considerations for RS:

In subjects with RS, assessment of disease in the bone marrow will distinguish changes due to RS or transformed lymphoma from changes due to the pre-existing CLL.

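### DCR counts stable disease with no minimum time from first dose, so an SD reading confined to a scan before the Week 12 window scores as disease control

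*Combined protocol and SAP*

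**What the plan says.** Section 8.4.1 defines DCR as "the proportion of subjects in the analysis population who have CR, PR, or SD at any time during the study prior to disease progression". Section 8.6.1.2 restates it as "the proportion of subjects in the analysis population who have achieved a CR, PR or SD response prior to disease progression". Table 8 lists DCR among the key secondary endpoints. It is reported as a point estimate with a 90% two-sided exact confidence interval, by central review (primary) and by investigator assessment.

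The response table in Section 12.7 gives SD as a residual category, "Failure to attain CR/PR or PD", with no time element.

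Section 7.1.2.7.4 sets the first response assessment at Week 12, with a 7-day window either side, and then every 12 weeks. Two provisions can produce a scan before that:

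- Section 7.1.2.7.4 adds that the first "assessment may be performed earlier than 12 weeks if, in the opinion of the investigator, the subject is clinically progressing".
- The flow chart in Section 6.1 marks both imaging and IWG response assessment at the discontinuation visit.

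Table 10 scores subjects with missing data as failures for DCR. Footnote a of the flow chart and Section 7.1.5.4 keep subjects who stop drug without progression on 12-weekly disease imaging.

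**The concern.** With no earliest qualifying date, one scan taken a few weeks after first dose can establish disease control if it falls short of the progression criteria. Early scans are not a random sample. One route selects subjects whom the investigator already believes to be progressing, and the other selects subjects who are stopping drug. If such a scan reads SD, later progression does not undo it, because the SD came first. The existing safeguard does not help, since an early SD reading is not missing data.

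Two subjects with the same early clinical failure can therefore be scored in opposite ways, depending only on whether a scan was done. What is at stake is the meaning of a reported secondary estimate. No test or decision depends on it.

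**Working it through.** **Inputs**

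- Earliest on-schedule scan: Week 12 minus 7 days (Section 7.1.2.7.4).
- Denominators: 50 treated subjects planned for rrPMBCL (Section 8.8); 24 RS subjects enrolled before that cohort closed (Section 2.1).
- Expected DCR, and the number of subjects whose only SD is early: not given anywhere.

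**Plan's own figures.** The plan states no DCR value to reproduce. For scale, Section 8.8 gives a maximum half-width of 12% for a 90% exact interval at n=50. Clopper-Pearson for 25/50 gives 37.6% to 62.4%, a half-width of 12.4 points, which agrees.

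**Step 1: what the schedule already implies.** 12 × 7 − 7 = 77 days, or 11 weeks. SD on an on-schedule scan already means about 11 weeks without documented progression.

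**Step 2: who is scored differently.** Compare the rule as written with one that counts SD only from day 77:

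| Subject | As written | SD from day 77 |
|---|---|---|
| SD at the scheduled Week 12 scan | controlled | controlled |
| Stops early, SD at discontinuation, still SD on a follow-up scan at or after day 77 | controlled | controlled |
| SD on an early scan only; then progression, death, new therapy or dropout before any later qualifying scan | controlled | not controlled |
| Same early failure, no post-baseline scan | not controlled (Table 10) | not controlled |

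Only the third row changes.

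**Step 3: direction.** Every subject controlled under the day-77 rule is also controlled under the written rule, and the reverse is not true. The written rule can therefore only give an equal or higher DCR.

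**Step 4: size per subject.** 1/50 = 2.0 percentage points; 1/24 = 4.2 percentage points. The 24 is an enrolment count. If fewer were treated, each subject weighs slightly more (1/23 = 4.3).

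**Step 5: illustration.** The base counts and the number reclassified, k, are assumptions chosen to show scale.

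| n | Base DCR (90% exact CI) | k | DCR after reclassifying k (90% exact CI) |
|---|---|---|---|
| 50 | 30/50 = 60% (47.4–71.7) | 1 | 29/50 = 58% (45.4–69.9) |
| 50 | 30/50 = 60% (47.4–71.7) | 3 | 27/50 = 54% (41.5–66.2) |
| 24 | 12/24 = 50% (31.9–68.1) | 1 | 11/24 = 45.8% (28.2–64.2) |
| 24 | 12/24 = 50% (31.9–68.1) | 3 | 9/24 = 37.5% (21.2–56.3) |

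With one to three such subjects the shift stays inside the sampling uncertainty of the estimate. Unlike sampling error, it has a fixed direction.

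**The case against.** The strongest reply is that the schedule already does most of the work. This stands: subjects scanned on time meet the proposed cut-off without any change, and the affected group is narrow.

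Several stronger readings are tempting, and the documents do not support them.

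- *Anyone who stops early for toxicity becomes a success.* Such subjects stay on 12-weekly imaging. One who is still stable at a later scan counts under either definition.
- *Footnote d of the flow chart proves the discontinuation route.* It contains the sentence "If previous scan was obtained within 4 weeks prior to the date of discontinuation, then a repeat scan at treatment discontinuation isn't mandatory", but it opens by addressing subjects with unconfirmed progression who stayed on drug. For them a later SD no longer precedes progression. The route rests on the discontinuation column of the flow chart, not on that sentence.
- *A deteriorating subject with 40% growth is always read as SD.* This depends on the measure. If both diameters of several nodes grow by 40%, the product rises by 96% (1.4² = 1.96), which exceeds the 50% threshold for progression in Section 12.7. A new lesion above 1.5 cm or new marrow involvement is also progression. For variably FDG-avid or PET-negative disease, the SD row requires unchanged lesion size on CT.
- *The inflation in RS can be estimated from the 3.5-month median progression-free survival in Section 4.2.1.2.* That figure comes from newly transformed patients on R-EPOCH, not relapsed or refractory patients on pembrolizumab. It also counts progression and death, not early SD scans. No document gives the share of early failures with such a scan.

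It is also fair to say that the any-time wording is explicit and parallels the response-rate definition. DCR carries no hypothesis or alpha. PFS, reported beside it, counts later progression or death whether or not drug was stopped, and its second sensitivity analysis treats new anticancer therapy as an event. Section 8.0 already allows the RS analyses to be modified. The Site Imaging Charter and the supplemental SAP were not available and might set a minimum. If so, it belongs in the endpoint definition.

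**Conclusion.** The point holds in a narrow form. As written, DCR accepts SD from any post-baseline scan before progression, the plan provides for scans before the Week 12 window, and no supplied text excludes an early-only SD reading. Compared with a Week 12 requirement, the effect on DCR is zero or upward: 2.0 points per affected subject at n=50 and 4.2 at n=24. The total cannot be stated, because the number affected is not derivable from the documents. A claim that DCR is materially inflated would go beyond the evidence.

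The conclusion assumes that neither the imaging charter nor the supplemental SAP sets a minimum SD time. It is a low-priority improvement to an estimated-only endpoint. The primary response rate, its test and its sample size do not depend on it.

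**What to change.** In Sections 8.4.1 and 8.6.1.2, state that SD counts toward DCR only if documented before progression and at or after the lower edge of the Week 12 window, 77 days from first dose, and that scans in off-treatment follow-up qualify. Complete or partial response continues to count at any time before progression. Treated subjects whose only SD is earlier count as not controlled. Keep the present any-time definition as a sensitivity analysis and report how many subjects differ between the two, which supplies the number missing here.

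The cost is one sentence, with no new visits, scans or data. The reported DCR may be slightly lower. Subjects with stable disease who leave before Week 12 for reasons unrelated to disease will count as not controlled; that is consistent with how Table 10 already treats missing data, and the sensitivity analysis shows its effect.

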8.4.2 Safety Endpoints

Safety measurements are described in Section 7.

8.5 Analysis Population

8.5.1 Efficacy Analysis Population

The analysis of primary efficacy endpoints are based on the All Subjects as Treated (ASaT) population, i.e., subjects will be included if they receive at least one dose of study medication (pembrolizumab).

Supportive analyses will be conducted in the Full Analysis Set (FAS) population, which consists of all subjects who 1) receive at least one dose of study medication; 2) have a baseline disease assessment, and 3) have a post baseline disease assessment or discontinue the trial due to PD/drug related AE.

